Duration of response (DR) will be defined as the duration from the first documentation of objective response to the first documented disease progression. The DR will be censored on the date of last tumor assessment documenting absence of disease progression for subjects who have no documented progression prior to data cutoff, dropout, or the initiation of alternate anticancer therapy. Duration of response will only be calculated for the subgroup of subjects with an objective response.

Time to progression (TTP) will be measured from the start of treatment with MEDI-575 until the documentation of disease progression. Disease progression is defined according to RECIST guidelines. The TTP will be censored on the date of last tumor assessment documenting absence of tumor progression for subjects who have no documented progression prior to data cutoff, dropout, or the initiation of alternate anticancer therapy. Subjects having no tumor assessments after the start of treatment with MEDI-575 will have TTP censored on the first date of treatment with MEDI-575.

Progression-free survival (PFS) will be measured from the start of treatment with MEDI-575 until the documentation of disease progression or death due to any cause, whichever occurs first. Disease progression is defined according to RECIST guidelines. The PFS will be censored on the date of last tumor assessment documenting absence of tumor progression for subjects who have no documented progression and are still alive prior to data cutoff, dropout, or the initiation of alternate anticancer therapy. Subjects having no tumor assessments after the start of treatment with MEDI-575 will have PFS censored on the first date of treatment with MEDI-575.

Overall survival (OS) will be determined as the time from the start of treatment with MEDI-575 until death. For subjects who are alive at the end of study or lost to follow-up, OS will be censored on the last date when subjects are known to be alive.

The time to event data including TTR, DR, TTP, PFS, and OS will be evaluated using Kaplan-Meier methods.

A select panel of biomarkers will be employed which may include evaluation of the effects of MEDI-575 on serum tumor biomarkers including prostate-specific antigen (PSA) and cancer

antigen125 (CA-125) or other tumor markers as determined by tumor type. Descriptive statistics will also be provided.

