**Cycle 2 and All Subsequent Cycles, Study Day 15 (Cohorts 1 through 5 and Weekly Dose-Expansion)**

- 1) Update concomitant medications
- 2) Blood collection prior to infusion of MEDI-575

- Chemistry panel (AST/ALT, total bilirubin, creatinine, alkaline phosphatase, sodium, potassium, chloride, phosphorus, calcium, glucose, magnesium, albumin, and LDH)
  - Hematology (CBC, differential, and platelet count)
  - Serum concentration of MEDI-575
  - Circulating plasma biomarker analysis
- 3) Routine urinalysis
  - 4) Vital signs prior to infusion of MEDI-575 (temperature, blood pressure, pulse rate, respiratory rate)
  - 5) Administration of MEDI-575
  - 6) Assessment of AEs and SAEs
  - 7) Monitor vital signs at 15, 30, and 45 minutes ( $\pm$  5 minutes) post initiation of infusion, at the completion of infusion ( $\pm$  5 minutes), and 30 and 60 minutes ( $\pm$  5 minutes) post completion of infusion
  - 8) Blood collection immediately after ( $\pm$  5 minutes) completion of infusion of MEDI-575
    - Serum concentration of MEDI-575
    - Circulating plasma biomarker analysis

**Every 2 Cycles (Within 3 Days Prior to Subsequent Cycle, Beginning With Cycle 3; All Dose Cohorts and Dose-Expansion Phase)**

*The following evaluations will be performed every 2 cycles (ie, every 6 weeks) unless otherwise indicated, beginning at Cycle 3 (eg, Cycle 3, Cycle 5, etc)*

- 1) Complete physical examination
- 2) Update concomitant medications
- 3) Assess for AEs and SAEs
- 4) Evaluation of disease
  - CT or MRI scans
  - Focused physical examination

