### **5.5.3 Antitumor Activity of MEDI-575**

The antitumor activity of MEDI-575 will be assessed based on ORR, TTR, DR, TTP, PFS, and OS.

The ORR is defined as the proportion of subjects with confirmed CR or confirmed PR according to RECIST guidelines. Confirmed responses are those that persist on repeat imaging study  $\geq 4$  weeks after the initial documentation of response.

The TTR will be measured from the start of treatment with MEDI-575 to the first documentation of objective response and will only be assessed in subjects who have achieved objective response.

The DR will be defined as the duration from the first documentation of objective response to the first documented disease progression. The DR will be censored on the date of last tumor assessment documenting absence of disease progression for subjects who have no documented progression prior to data cutoff, dropout, or the initiation of alternate anticancer therapy. The DR will only be calculated for the subgroup of subjects with an objective response.

The TTP will be measured from the start of treatment with MEDI-575 until the documentation of disease progression. Disease progression is defined according to RECIST guidelines. The TTP will be censored on the date of last tumor assessment documenting absence of tumor progression for subjects who have no documented progression prior to data cutoff, dropout, or the initiation of alternate anticancer therapy. Subjects having no tumor assessments after the start of treatment with MEDI-575 will have TTP censored on the first date of treatment with MEDI-575.

The PFS will be measured from the start of treatment with MEDI-575 until the documentation of disease progression or death due to any cause, whichever occurs first. Disease progression is defined according to RECIST guidelines. The PFS will be censored on the date of last tumor assessment documenting absence of tumor progression for subjects who have no documented progression and are still alive prior to data cutoff, dropout, or the initiation of alternate anticancer therapy. Subjects having no tumor assessments after the start

of treatment with MEDI-575 will have PFS censored on the first date of treatment with MEDI-575.

The OS will be determined as the time from the start of treatment with MEDI-575 until death. For subjects who are alive at the end of study or lost to follow-up, OS will be censored on the last date when subjects are known to be alive.

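### The PFS paragraph contradicts itself on early deaths: the Day 1 censoring sentence for subjects without a tumor assessment has no condition that the subject be alive

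*Protocol*

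**What the plan says.** Section 5.5.3 measures PFS from the start of treatment "until the documentation of disease progression or death due to any cause, whichever occurs first". It then gives two censoring sentences.

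- The general sentence censors at the last progression-free tumor assessment. It covers subjects who have no "documented progression and are still alive prior to data cutoff", dropout or alternate anticancer therapy, so it applies only to the living.
- The second sentence deals with subjects who have no post-baseline tumor assessment. They "will have PFS censored on the first date of treatment with" MEDI-575. It says nothing about vital status.

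The Study Abstract (Assessment of Endpoints) repeats the second sentence: "Subjects having no tumor assessments after the start of treatment with MEDI-575 will have PFS censored on the first date of treatment with MEDI-575".

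The TTP paragraph of Section 5.5.3 ends in the same form: such subjects "will have TTP censored on the first date of treatment with MEDI-575". Death is not a TTP event.

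On timing, Section 3.6 introduces the on-treatment disease evaluation with "The following evaluations will be performed every 2 cycles (ie, every 6 weeks", starting at Cycle 3.

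**The concern.** A subject who dies before any post-baseline tumor assessment meets the PFS event definition and also falls within the Day 1 censoring sentence. Nothing in the protocol says which prevails, so two analysts could draw different PFS curves from the same data.

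The general sentence does not plainly settle the matter. It places censoring at a last tumor assessment, a date that these subjects lack, so the second sentence reads as the specific rule for exactly this group. It suits TTP. Applied to PFS, it turns an event into a censoring at time zero.

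The error would run in one direction. The earliest deaths are the worst PFS outcomes, and removing them can only raise the curve. The setting makes some early deaths possible: refractory disease, Karnofsky status down to 60, and a first scheduled scan at about week 6, or about week 7 in Cohort 1, whose first cycle lasts 28 days. PFS is a named measure of antitumor activity. Section 4.9 lets efficacy data, when available, inform the expansion doses, and Section 2.4 foresees comparing the two regimens in expansion groups of about 6.

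**Working it through.** **The text, clause by clause, for a subject who dies before any post-baseline assessment**

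| Clause | Result |
|---|---|
| Event definition | Event on the date of death |
| General censoring sentence | Does not apply, because the subject is not alive |
| No-assessment sentence, read literally | Censored on Day 1 |

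The first two clauses agree with each other; the third does not.

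**Inputs from the protocol**

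- Time-to-event endpoints are analysed by Kaplan-Meier methods (Section 5.5.3).
- The only related figure is the escalation sample size (Section 5.2), and it reproduces: 7 cohorts × 3 = 21 and 7 × 6 = 42. Adding 12 expansion subjects gives 33 to 54.
- No PFS rate, median, event count or early-death rate is stated.

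**Formula**

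Take n subjects, of whom k die before any assessment, with no other censoring. Let x be the number event-free at a time t after those deaths.

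- Deaths counted as events: S(t) = x/n.
- Deaths censored at time zero: these subjects leave before the first event and enter no risk set, so S(t) = x/(n-k).
- Ratio = n/(n-k) = 1/(1-d), where d = k/n.

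Hence 1/0.97 = 1.03 at d = 3%, 1/0.90 = 1.11 at 10%, and 1/0.80 = 1.25 at 20%.

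**Scenarios**

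These are assumptions, not protocol figures: the remaining subjects have exponential PFS with a 12-week median, deaths are spread over weeks 1 to 5.5, and there is no other censoring.

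| n | Early deaths | 6-week PFS, deaths as events | 6-week PFS, Day 1 censoring | Median PFS in weeks, events vs Day 1 censoring |
|---|---|---|---|---|
| 33 | 1 | 23/33 = 69.7% | 23/32 = 71.9% | 11.5 vs 11.5 |
| 33 | 3 | 21/33 = 63.6% | 21/30 = 70.0% | 10.3 vs 11.4 |
| 33 | 5 | 20/33 = 60.6% | 20/28 = 71.4% | 9.2 vs 11.4 |
| 33 | 7 | 18/33 = 54.5% | 18/26 = 69.2% | 7.9 vs 11.3 |
| 54 | 5 | 35/54 = 64.8% | 35/49 = 71.4% | 10.0 vs 12.0 |

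In an expansion group of 6 with one early death and five subjects event-free at week 6, the two readings give 5/6 = 83% and 5/5 = 100%.

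**Range for d**

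With exponential OS of median M weeks, the share dying before week 6 is 1 - 0.5^(6/M): 29%, 16%, 11% and 8% for M = 12, 24, 36 and 52. These are upper limits for d under each assumed M, because some of these subjects will have had an assessment before death.

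**The case against.** The best defence is to read the paragraph as a whole. It has just made death an event and confined censoring to the living. The last sentence can then be taken as supplying a date for subjects who already qualify for censoring but have no last assessment. On that reading early deaths are events and nothing is overstated. The reading is reasonable, and it rules out the stronger conclusion that a reader might draw: that the protocol settles on censoring early deaths and that reported PFS will be too high. The documents support only a conflict that leaves Day 1 censoring open. The defence does not remove that conflict, because the sentence is unconditional and nothing subordinates it to the definition.

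The affected group is also narrower than subjects who die before the first scheduled scan. The sentence speaks of tumor assessments, which under Section 3.7.5 may include physical examination and chest x-ray. The End of Treatment visit includes CT or MRI and can fall before week 6. Eligibility requires a life expectancy of at least 12 weeks, twice the time to the week-6 evaluation. These points reduce d but do not make it zero: a subject who dies on treatment may never reach an End of Treatment visit.

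Nor is every PFS estimate affected, only one that includes such a death. One in 33 moves 6-week PFS by about 2 points and leaves the median unchanged. Section 5.5.3 does not call for PFS curves by dose cohort, so an argument from cohorts of 3 would go beyond the text.

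Finally, Section 5.1 promises a statistical analysis plan, the usual home for censoring detail. Here, however, the protocol states the rule itself, so that plan would have to override it.

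**Conclusion.** The point holds as an internal inconsistency, in Section 5.5.3 and in the Abstract. Followed literally, the no-assessment sentence censors at Day 1 a subject who dies before any post-baseline tumor assessment, and any Kaplan-Meier PFS estimate that includes a share d of such subjects is inflated by 1/(1-d). If the event definition governs, there is no inflation.

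The factor is exact with no other censoring and at times after the early deaths. Its size in this trial cannot be fixed from the documents. In the 12-week-median scenarios above, the median shifts by between 0 and about 3.4 weeks.

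The consequence is limited. PFS is one of six secondary antitumor measures, summarised without a stated hypothesis or threshold. OS counts every death, and the DLT and MTD rules do not use PFS. The sentence should be corrected before PFS is analysed, but it does not threaten the primary objectives.

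**What to change.** In Section 5.5.3 and in the Abstract, replace the no-assessment sentence for PFS with wording such as: *A subject who is alive and has had no post-baseline tumor assessment is censored for PFS at the first dose. A subject who dies without a post-baseline tumor assessment has a PFS event on the date of death.* The alive condition should match that of the preceding general sentence, so that dropout and alternate anticancer therapy are handled in the same way in both. Leave the TTP sentence unchanged.

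The cost is one sentence in two places. No new data are needed, since Section 3.6 already follows survival status in all subjects until death or the end of the study. The downside is that PFS may come out slightly less favourable.

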## **6 Data Collection and Monitoring**

The study will be monitored by MedImmune or its designee on a regular basis throughout the study period. During monitoring visits, the investigator will provide direct access to all source documentation relevant to the subject's participation in the study. Source documentation includes, but is not limited to, the subject's clinic and/or office chart, hospital chart, informed consent forms, treatment notes, laboratory reports, pharmacy records, radiographs, and any other records maintained to conduct and evaluate the clinical study. The investigator must also ensure that direct access to study documents be made available for study-related audits, IRB/IEC review, or regulatory inspection.

Data recorded on source documents will be transcribed onto a validated data collection instrument (a paper case report form or electronic data screen) provided by MedImmune or its designee. The investigator must ensure the accuracy and completeness of the data reported, and its consistency with the source documentation.

The primary source document for this study will be the subject's medical records. If separate research records are maintained by the investigator(s), both the medical record and the research records will be monitored/audited for the purposes of the study.

Study documents (including subject records, copies of collected data, study notebook, and pharmacy records) must be kept secured in accordance with MedImmune policies and applicable regulatory requirements for a period of 2 years following marketing of MEDI-575 or for 2 years after centers have been notified that the study has been closed and the IND has

been discontinued. There may be other circumstances for which MedImmune is required to maintain study records and, therefore, MedImmune should be contacted prior to removing study records for any reason.

## **7 Human Subjects**

### **7.1 Ethics and Regulatory Considerations**

The study will be conducted according to the Declaration of Helsinki, the International Conference on Harmonisation (ICH) guidelines on Good Clinical Practice (GCP), Protection of Human Subjects (21 CFR Part 50), Institutional Review Boards (21 CFR Part 56), and Investigational New Drug Application (21 CFR Part 312).

The protocol will be reviewed and approved by the Institutional Review Board (IRB) or Independent Ethics Committee (IEC) of each participating center prior to study initiation. Serious adverse events regardless of causality will be reported to the sponsor and to the IRB/IEC, and the investigator will keep the IRB/IEC informed as to the progress of the study.

The investigator will explain the nature of the study and will inform the subject/legal representative that participation is voluntary and that they can withdraw/can withdraw their child at any time. Written informed consent will be obtained from each subject/legal representative prior to the screening procedures required for entry into the study. A copy of the signed consent form will be given to every subject/legal representative and the original will be maintained with the subject's records.

To maintain confidentiality, all laboratory specimens, evaluation forms, reports and other records will be identified by a coded number and initials only. All study records will be kept in a locked file cabinet and code sheets linking a subject's name to a subject identification number (SID) will be stored separately in another locked file cabinet. Study records may be maintained electronically and require the same security and confidentiality as paper. Clinical information will not be released without written permission of the subject/legal representative, except as necessary for monitoring by regulatory authorities or the sponsor of the clinical study. The principal investigator must also comply with all applicable privacy regulations (eg, HIPAA 1996, EU Data Protection Directive 95/46/EC).

## **7.2 Institutional Review Board (IRB) or Independent Ethics Committee (IEC)**

A list of IRB/IEC members should be obtained by the investigator and provided to the sponsor.

Any documents that the IRB/IEC may need to fulfill its responsibilities, such as protocol amendments, and information concerning subject recruitment, payment or compensation procedures, or information from the sponsor will be submitted to the IRB/IEC. The IRB/IEC's written unconditional approval of the study protocol, the informed consent form, and any other written materials to be provided to subjects will be in the possession of the investigator and the sponsor before the study is initiated. The IRB/IEC's unconditional approval statement will be transmitted by the investigator to the sponsor prior to shipment of investigational product supplies to the site. This approval must refer to the study by exact protocol title and number, and should identify the documents reviewed and the date of review.

Protocol modifications or changes may not be initiated without prior written IRB/IEC approval except when necessary to eliminate immediate hazards to the subjects or when the change(s) involves only logistical or administrative aspects of the study. Such modifications will be submitted to the IRB/IEC and written verification that the modification was submitted should be obtained.

The IRB/IEC must be informed by the investigator of informed consent form changes or revisions of other documents originally submitted for review; serious and/or unexpected adverse experiences occurring during the study; new information that may affect adversely the safety of the subjects or the conduct of the study; an annual update and/or request for re-approval; and when the study has been completed.

## **7.3 Informed Consent**

The principles of informed consent in the Declaration of Helsinki should be implemented before any protocol-specified procedures or interventions are carried out. Informed consent will be obtained in accordance with 21 Part CFR 50 and any applicable local regulations.

Information should be given in both oral and written form, and subjects or their legal representatives must be given ample opportunity to inquire about details of the study. The written informed consent document will embody the elements of informed consent as described in the Declaration of Helsinki and will also comply with local regulations.

Subjects or their legal representatives must be informed that the study involves research. They must be informed about the aims, expected benefits, possible risks (including a statement that the particular treatment or procedure may involve risks to the subject or the fetus of the subject, if the subject should become pregnant) that are currently unforeseeable. They must also be informed of the study procedures to be followed and alternative treatment available to them. Subjects or their legal representatives must receive an explanation as to whether any compensation and any medical treatments are available if injury occurs and, if so, what they consist of, or where further information may be obtained. They must be informed whom to contact for answers to any questions relating to the research project. The subjects or their legal representatives must be informed that participation is voluntary and that they are free to withdraw or withdraw their child from the study for any reason at any time, without penalty or loss of benefits to which they are otherwise entitled. The extent of the confidentiality of subject records must be defined, and subjects or their legal representatives must be informed that applicable data protection legislation will be complied with. They must be informed that the monitor(s), auditor(s), IRB/IEC members, and the regulatory authorities will be granted direct access to the subject's original medical records for verification of clinical study procedures and/or data, without violating the confidentiality of the subject, to the extent permitted by the applicable laws and regulations and that, by signing a written informed consent form, the subject or the subject's legally acceptable representative is authorizing such access.

The consent form generated by the investigator must be approved by the IRB/IEC and be acceptable to MedImmune. Consent forms must be written so as to be understood by the prospective subject/legal representative. Informed consent will be documented by the use of a written consent form approved by the IRB/IEC and signed and dated by the subject or the subject's legally authorized representative, and by the person who conducted the informed consent discussion. The signature confirms the consent is based on information that has been understood. Each subject's signed informed consent form must be kept on file by the investigator for possible inspection by Regulatory Authorities and/or MedImmune professional and Regulatory Compliance persons. The subject or the subject's legally acceptable representative should receive a copy of the signed and dated written informed consent form and any other written information provided to the subject, and should receive copies of any signed and dated consent form updates and any amendments to the written information provided to subjects.

## **8 Study Completion**

Study completion is defined as the date of the last assessment for the last subject in the study.

All materials or supplies provided by the sponsor will be returned to the sponsor upon study completion. The investigator will notify the IRB/IEC when the study has been completed.

